Screening. At this initial screening visit (T0), consent forms will be reviewed, eligibility confirmed, and a Clinical and Health Screening will be completed. Women will be required to have a GYN exam within the past year. Women who have had this exam completed already will be asked to provide medical records for review. Women who have not had this exam within the past year can go to their own provider to complete the exam—providing the records for review—or can be scheduled to see the study GYN ([name]). This screening will include a laboratory panel (CMP, CBC, pregnancy test). After enrollment (if eligible), participants will complete the Daily Rating Form for one natural menstrual cycle. This form will be completed each morning, throughout the study duration. We expect the completion of the Daily Rating Form to take <5 minutes. The Daily Rating Form will also be used to monitor subject safety regarding changes in mood and eating disorder symptoms throughout the protocol.

Baseline (T1) and end-of-phase assessments (T2-T4). Prior to beginning the reproductive hormone challenge, participants will complete a baseline assessment (T1) including self-report questionnaires and behavior tasks. Most procedures will be repeated at the end of each experimental phase: after 6-weeks of Lupron (T2); after 2-weeks of E2/P4 (T3/T4). After the baseline assessment, subjects will complete three end-of-phase assessments.

Check-in Visits. In addition to the Daily Rating Form, subjects will have study visits (either end-of-phase or check-in visits) every two weeks. Check-in visits will be completed in order to assess side effects and protocol adherence. Two check-in visits will occur during Lupron only before medication administration begins and one will occur during medication administration (after the washout period). The number of check-in visits and end-of-phase assessments are standardized across the study protocol. The same adherence, monitoring, and side-effect checks will occur at every study visit once medication administration begins. Along with monitoring side effects and adherence, this information will be used for protocol development in our future studies. From these visits, we can pinpoint when ovarian suppression has occurred, and thus, the protocol could be modified for future studies based on this information.

Medication Administration and Study Visits. The first dose of Lupron will be given at T1 and monthly thereafter. Medication administration (placebo, E2, or P4) will begin after 4-weeks of Lupron alone. Subjects will be blinded as to whether capsules contain placebo, E2, or P4. Investigators will be blinded to the order of E2 and P4. Subjects will be told that at some points the medication will be active and at other points the medication will be inactive. Once medication administration begins, participants will have four remaining study visits; three end-of-phase assessments and one check-in visit. The behavioral tasks that are part of the end-of-phase assessments are the primary difference between the end-of-phase visits and the check-in visit (we believe participants would be unlikely to notice small differences in the type and number of self-report questionnaires given). Participants will be told that, over the final 8-weeks of the study, they will attend three long study visits and one short study visit, and the addition of the behavioral tasks to the study visit will be randomly scheduled. They will be informed of the next study visit type at their current study visit. Although the assignment of the behavioral tasks is not random, this is done in order to ~~decrease~~ the likelihood that the participant would detect

whether they are on inactive or active medication by the timing and duration of the study visits. Given the significant length of time the addition of the behavioral tasks adds to the study visits (~ 60 minutes), it would add significant and unreasonable participant burden to add the behavioral tasks to the post-washout period visit, with no empirical/scientific justification to do so given we are not addressing symptom change on the behavioral tasks during the washout period.

Follow-up. Eight weeks after study completion a brief follow-up assessment, via online self-report questionnaire, will be completed by participants.

7 Statistical Plan

[name] is the database manager and [name], is the biostatistician who will complete the statistical analyses.

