Fourth, to further ensure the safety of enrolled subjects, participants will complete bi-weekly assessments of change in physical symptoms, mood, suicide risk, and eating disorder symptoms throughout the hormone manipulation—this is in addition to the daily assessment. Mood symptoms and suicide risk will be monitored by administering the Inventory of Depression and Anxiety Symptoms (IDAS). The IDAS will be scored immediately and if IDAS suicidality risk scores > 8 are observed (mean score observed in non-psychiatric community sample; we use this mean to conservatively evaluate risk¹⁸⁰), then the Hamilton Rating Scale for Depression and SSI will be administered as described above. BN symptoms (e.g., binge eating, purging) will be monitored at bi-weekly appointments with the Eating Disorder Examination Questionnaire (EDEQ). The EDEQ will be scored during bi-weekly visits and scores will be compared with baseline levels and previous study visits. [name] will follow-up with any participant with a $>50\%$ increase in symptoms as indicated by the EDEQ questions regarding frequency of binge eating and purging behaviors.

We are not conducting a clinical treatment study and thus are not providing care or management of the subject's BN symptoms. We will not provide treatment or pay for treatment/medical costs for subjects who are discontinued from the study or in need of medical care during the course of the study. However, we will ensure subjects have appropriate treatment contacts before terminating contact with the subject.

Notably, no serious adverse reactions or events were encountered in past studies conducted with this protocol. No subjects to date have been discontinued from a study protocol due to heightened suicide risk. Indeed, this is true of similar experimental designs that have been longer in nature and selected individuals with a history of a mood disorder. It is possible that women with current BN may be at increased risk; however, this risk is decreased by excluding women with a significant suicide history. Additionally, previous studies implementing this hormone regimen have shown that E2 and P4 addback are the conditions which negatively impact mood^{87, 118} (i.e., depressive symptoms worsen). In the current study these conditions are brief, lasting only 2-weeks. Thus, any impact on mood that may occur is expected to be transient.

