This also standardizes each study phase to be 2-weeks in length as the first month of Lupron is not a study phase of interest, yet a ‘waiting period’ for ovarian suppression to occur.

Table 4. Study Visit Procedures

| Procedure | T0 | T1 | T2 | T3 | T4 | T5 | Check-in |
|-----------------------------------|----|----|----|----|----|----|----------|
| Eligibility and Enrollment | | | | | | | |
| Informed Consent | x | | | | | | |
| Demographics | x | | | | | | |
| SCID-5 | x | | | | | | |
| GYN Exam/Medical History | x | | | | | | |
| Venipuncture | x | | | | | | |
| Saliva Samples | | x | x | x | x | | x |
| Side Effects & Adherence | | | x | x | x | | x |
| Self-report Questionnaires | | | | | | | |
| IDAS* | x | x | x | x | x | x | x |
| EDEQ* | x | x | x | x | x | x | x |
| EPSI | x | x | x | x | x | x | x |
| BIS/BAS | | x | x | x | x | x | x |
| SPSRQ | | x | x | x | x | x | x |
| Behavioral Tasks | | | | | | | |
| MIDT | | x | x | x | x | | |
| DD | | x | x | x | x | | |
| Go/No Go | | x | x | x | x | | |
| PANAS | | x | x | x | x | | |
| 24-hour Food Intake | | x | x | x | x | | |

*used to monitor subject safety only

Induced Hypogonadism. At T1, participants will receive their first injection of the gonadotropin-releasing hormone (GnRH) agonist leuprolide acetate (Lupron) 3.75 mg/month via i.m. injection, which is administered to produce a stable hypogonadal condition (after the initial “flair”). The first Lupron injection will be administered at approximately day six of the participants’ first menstrual cycle and monthly thereafter. Subjects will be on Lupron alone for 6-weeks. Previous studies using this experimental design show significant change in behavioral measures of interest after 6-weeks.⁸⁷

During the first month of GnRH agonist administration, participants will not receive any other medication. After 4-weeks of Lupron alone, all participants will receive 2-weeks of placebo capsules (blinded to the participant) and continue daily capsules throughout the duration of the study. Subjects will be told at some points the medication will be active and at other points it will be placebo. Subjects will not know when medication is active vs. placebo. An end-of-phase (T2) assessment will occur before addback, 2-weeks after medication administration begins.

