Addback. After 6-weeks of Lupron-alone treatment (i.e., hypogonadism), physiological levels of E2 or P4 will be attained via oral micronized E2 (2mg b.i.d) or P4 (200mg b.i.d), respectively (along with continued Lupron administration), with a 2-week washout period in-between. Placebo pills continue during the washout. Each addback phase will be 2-weeks (compared with 4-weeks) as previous studies using this experimental design have shown significant symptom change can be obtained within 2-weeks.⁸⁷ Subjects will be randomized to receive E2 followed by P4 or P4 followed by E2. The study biostatistician will create a randomization table and study investigators will be blinded to the randomization order. End-of-phase assessments will occur at the end of E2 and P4 addback (T3/T4).

Once medication administration begins, subjects will be instructed to take pills twice daily, at approximately the same time each day. To improve medication compliance, we will recommend subjects schedule a daily reminder on their phone to take the study medication each day. The daily assessments will also ask participant’s whether they took the study medication each day.

Clinical Assessments. Measures used to obtain primary outcomes and monitor subject safety are shown in **Table 4**. Study visits will occur every 2-weeks. Participants will attend end-of-phase assessments at the end of each hormone phase as well as check-in visits to monitor symptoms. There will be an equal number of end-of-phase assessments and check-in visits (3 each) during the hormone challenge. All study measures are empirically valid and reliable.

Clinical Interviews

- a) **SCID-5:** Structured Clinical Interview for DSM-5¹⁸¹ will be administered by trained study staff at T0, and supervised by [name], to confirm eligibility and BN diagnosis. Based on DSM-5 criteria, the interview guides trained interviewers in determining whether a psychiatric diagnosis is present or absent.

Self-report Questionnaires

Self-report questionnaires will be completed through secure, encrypted, online survey (i.e., Qualtrics), and scored by standard conventions. During the reproductive hormone challenge, (i.e., T1-T4) self-report questionnaires will be modified to represent symptomatology over the previous week only, in order to capture the period of time with maximal or minimal pathology during each hormone manipulation phase.

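### The one-week recall in Section 6 also falls on the safety-only IDAS and EDEQ, so these two-weekly forms skip alternate weeks, including the first week on each hormone; the daily form narrows the gap, mainly to purging

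*Combined protocol and SAP*

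**What the plan says.** Section 6, under Self-report Questionnaires, states that during the challenge (given as T1-T4) "self-report questionnaires will be modified to represent symptomatology over the previous week only", and gives the reason: "in order to capture the period of time with maximal or minimal pathology during each hormone manipulation phase". IDAS and EDEQ are in the list that follows and under the same heading in Table 4, at T0 to T5 and at every check-in. The table's footnote marks both as "used to monitor subject safety only". Nothing exempts them from the rewording.

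On timing, Section 6 says "Study visits will occur every 2-weeks", with three check-ins and three end-of-phase visits after T1.

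On safety, Section 4.4.1 says "participants will complete bi-weekly assessments of change in physical symptoms, mood, suicide risk, and eating disorder symptoms throughout the hormone manipulation", and adds that "this is in addition to the daily assessment". Two triggers are attached to this bi-weekly layer:
- an IDAS suicidality score above 8 leads to further scales;
- an increase of more than 50% in binge or purge frequency, read from the EDEQ against baseline and earlier visits, leads to follow-up.

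The daily form is described in Section 4.4.1 and in Section 6 (Daily Symptom Assessment, Screening). It is completed every morning from T0 to T4 and sent to the team in real time. It covers mood, suicide-risk items and bulimia symptoms, with binge frequency as the example. A missed form leads to a telephone safety assessment.

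**The concern.** A recall window chosen to isolate the outcome week of each phase has been applied, as written, to two forms that measure no outcome. With a two-week visit interval and a one-week look-back, each visit leaves the earlier of the two preceding weeks unasked.

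The skipped weeks are not arbitrary. They include the first week on each hormone and the first week after the first hormone stops. Section 4.4.1 itself reports that in earlier studies the addback conditions worsened mood, and expects any such effect here to be transient. Section 1.1 raises the possibility that sensitivity is to changing hormone levels rather than to their presence. A short reaction to a change is what a last-week-only form at the end of a two-week phase can miss.

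At stake is the second safety layer: its two triggers work on half of the challenge weeks. The first layer, the daily form, still runs.

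**Working it through.** **Inputs.** Visits every two weeks (Section 6, Clinical Assessments). Lupron starts at T1, capsules after 4 weeks, T2 after 6 weeks; each addback lasts 2 weeks, with a 2-week washout between (Sections 5.2 and 6). Two check-ins fall before capsules start and one after the washout (Section 6, Check-in Visits).

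**Schedule check.** Setting T1 at week 0 gives check-ins at weeks 2, 4 and 10, T2 at week 6, T3 at week 8 and T4 at week 12. With T0 this makes 1 + 7 = 8 visits, as Section 3.1 states. Four of them (T2, T3, one check-in, T4) come after capsules start, as Section 6 states.

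**Coverage with a one-week look-back at every visit.**

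| Weeks | Phase | Visit | Week asked about | Week not asked about |
|---|---|---|---|---|
| 1-2 | Lupron alone | check-in | 2 | 1 |
| 3-4 | Lupron alone | check-in | 4 | 3 |
| 5-6 | Lupron plus placebo capsules | T2 | 6 | 5 |
| 7-8 | first hormone | T3 | 8 | 7 |
| 9-10 | washout | check-in | 10 | 9 |
| 11-12 | second hormone | T4 | 12 | 11 |

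Not asked about: 6 of 12 weeks, or 6 × 7 = 42 of 84 days (50%). This includes 2 of the 4 active-hormone weeks (7 and 11) and 1 of the 2 washout weeks (9).

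**Narrow reading.** Suppose T1-T4 means only those four visits, and check-ins keep a window of at least two weeks. The documents give no such window, so this is an assumption. Check-ins then recover weeks 1, 3 and 9. Weeks 5, 7 and 11 remain unasked: 3 of 12 weeks, or 21 of 84 days (25%), and still 2 of the 4 active-hormone weeks.

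**What the daily form covers.** It is scheduled on all 84 days, so 0 of 12 weeks lack planned monitoring of mood, suicide risk and binge frequency. Purging is in the EDEQ check but is not named among the daily items. No numeric rule for worsening bulimia symptoms is tied to the daily form. EPSI has a purging subscale, but it carries the same one-week wording and is not designated for safety review.

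**Why a two-week average is not the remedy.** Let the weekly baseline count be b. If one week rises by a fraction X and the other stays at b, the two-week mean is [b(1 + X) + b]/2 = b(1 + X/2). This exceeds 1.5b only if X is above 1. A one-week rise would have to pass 100% before a 50% check saw it, and that would hold in the last week of a phase too, where a rise above 50% is seen now. Comparing each week with b keeps the last-week sensitivity and adds the earlier week.

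**The case against.** The strongest reply is that little is lost. The daily form is the first layer, covers mood as well as suicide risk and binge frequency, reaches staff in real time, and is chased by telephone when missed. Section 6 (Screening) says it also monitors eating disorder symptoms. Side-effect checks take place at visits from T2 and at check-ins. This stands, and it rules out three stronger readings that a reader might infer:

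- *Participants are unmonitored in alternate weeks.* They are not; only IDAS and EDEQ skip those weeks.
- *The plan breaks its own promise of monitoring throughout the manipulation.* Section 4.4.1 promises bi-weekly assessments throughout, and they do take place at each bi-weekly visit. It does not promise that their recall covers every day.
- *Purging is not captured daily.* Binge frequency is only an example of the added daily items. The text supports no more than that daily purging items are not stated. In addition, the 50% rule in the withdrawal list of Section 4.4.1 covers purging and names no instrument; only the bi-weekly check cites the EDEQ.

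There is also doubt about scope. Appendix B says IDAS and EDE-Q were on paper before COVID, while the paragraph with the one-week wording describes online questionnaires, so it may not have been written with them in mind. But Appendix B moves both forms online and keeps that option, so staff following the current text would apply the one-week wording to them. The doubt is a reason to state the window.

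**Conclusion.** As written, the outcome-driven recall window extends to two safety-only forms and leaves 6 of 12 challenge weeks outside both, or at least weeks 5, 7 and 11 on the narrow reading. Half of the active-hormone time is outside on either reading.

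The consequence is limited. The IDAS trigger and the EDEQ 50% check cannot register a change confined to a skipped week, and purging is the symptom for which no other stated instrument clearly fills in. The conclusion rests on reading the Section 6 sentence literally; the narrow count also rests on an assumed check-in window. It is a point of minor to moderate weight about the reach of the second safety layer.

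**What to change.** 1. In Section 6, limit the one-week wording to the outcome scales: EPSI, BIS/BAS and SPSRQ.
2. Give IDAS a two-week look-back at T1-T4 and at every check-in.
3. Have EDEQ record binge and purge counts separately for each of the two preceding weeks, also at T1, so that every visit uses the same unit. Compare each week's count with the weekly baseline instead of averaging the two weeks.
4. Reconcile the withdrawal list and the bi-weekly check in Section 4.4.1 with the Daily Symptom Assessment text in Section 6: state whether daily-form data feed the 50% check, and whether that form asks about purging.

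The thresholds are left to the investigators. With a two-week look-back the two forms would cover 12 of 12 weeks (84 of 84 days).

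The cost is the wording of two forms, a few extra EDEQ items and slightly less exact recall for the earlier week. The plan gives both forms a safety role only, so no outcome analysis changes.

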[figure not shown]

Figure 3. Structural formula for leuprolide acetate (5-oxo-L-proyl-L-histidyl-L-tryptophyl-L-seryl-L-tyrosyl-D-leucyl-L-leucyl-L-arginyl-N-ethyl-L-prolinamide acetate).

LUPRON DEPOT is available in a prefilled dual-chamber syringe containing sterile lyophilized microspheres which, when mixed with diluent, become a suspension intended as a monthly intramuscular injection.

The front chamber of LUPRON DEPOT 3.75 mg prefilled dual-chamber syringe contains leuprolide acetate (3.75 mg), purified gelatin (0.65 mg), DL-lactic and glycolic acids copolymer (33.1 mg), and D-mannitol (6.6 mg). The second chamber of diluent contains carboxymethylcellulose sodium (5 mg), D-mannitol (50 mg), polysorbate 80 (1 mg), water for injection, USP, and glacial acetic acid, USP to control pH. During the manufacture of LUPRON DEPOT 3.75 mg, acetic acid is lost, leaving the peptide.

Pharmacology

Leuprolide acetate is a long-acting GnRH analog. A single monthly injection of LUPRON DEPOT 3.75 mg results in an initial stimulation followed by a prolonged suppression of pituitary gonadotropins.

Repeated dosing at monthly intervals results in decreased secretion of gonadal steroids; consequently, tissues and functions that depend on gonadal steroids for their maintenance become quiescent. This effect is reversible on discontinuation of drug therapy. Leuprolide acetate is not active when given orally. Intramuscular injection of the depot formulation provides plasma concentrations of leuprolide over a period of one month.

PROGESTERONE

Description

PROMETRIUM (progesterone, USP) Capsules contain micronized progesterone for oral administration.

Progesterone has a molecular weight of 314.47 and a molecular formula of C₂₁H₃₀O₂. Progesterone (pregn-4-ene-3, 20-dione) is a white or creamy white, odorless, crystalline powder practically insoluble in water, soluble in alcohol, acetone and dioxane and sparingly soluble in vegetable oils, stable in air, melting between 126° and 131°C. The structural formula is:

[figure not shown]

Figure 4. Structural formula for progesterone, USP (pregn-4-ene-3, 20-dione)

Progesterone is synthesized from a starting material from a plant source and is chemically identical to progesterone of human ovarian origin. PROMETRIUM Capsules are available in multiple strengths to afford dosage flexibility for optimum management. PROMETRIUM Capsules contain 200 mg micronized progesterone.

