- 6) **NC TraCS Research Recruitment Service:** We will capitalize on the TraCS Research Recruitment Service's expertise in enrolling members of communities historically under-represented in research.
- 7) **TrialFacts Clinical Trial Recruitment:** As of March 2021, we will also work with the clinical trial recruitment/marketing company TrialFacts. During recruitment and initial screening process, direct interaction occurs between the individual and TrialFacts, not study staff. The TrialFacts website specifically informs individuals that they are a distinct company from the trial site and a distinct organization from the site conducting the research study. Individuals consent to provide their data to TrialFacts, receive communication from TrialFacts, and for TrialFacts to provide us with their contact information. TrialFacts are the owners of the

data they collect and it does not become part of the research study data. TrialFacts primarily recruits via social media avenues (facebook, youtube, instagram etc). Individuals are self-identified by responding to the advertisements. Once an individual self-identified by TrialFacts is determined as potentially eligible for our study, contact information is provided to us by Trialfacts - only at this point does our study team begin/initiate any contact (i.e., phone call) with this individual.

Eligibility screening will include:

- An initial phone or online screening that includes questions about past medical and mental health history to assess potential participants eligibility based on the criteria listed in sections 4.1 and 4.2.
- Participants will undergo a Clinical and Health Screening process to determine whether they are healthy enough to participate in this study.
- All participants will receive a pregnancy test. No pregnant women will be entered into the study, because the study drugs (Lupron, estrogen, and progesterone) may be associated with birth defects.

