4.4 Early Withdrawal of Subjects

4.4.1 When and How to Withdraw Subjects

- Participants with significant clinical/laboratory abnormalities will not be enrolled/discontinued from the study prior to GnRH agonist administration.
- Participants deemed at elevated suicide risk at enrollment will not be enrolled in the study.
- If a subject is deemed at elevated suicide risk at any point after enrollment, they will be discontinued from the study protocol.
- Any subject experiencing clinically significant side effects that cannot be relieved will be discontinued.
- If menopausal-like symptoms occurring secondary to GnRH agonist treatment are intolerable, drug treatment will be discontinued.
- Any subject experiencing > 50% increase in BN symptom severity, as indicated by the frequency of binge eating and/or purging behaviors, during the medication protocol will be assessed for discontinuation. Continuing/discontinuing will, in part, depend on subject safety, whether the increase in severity is likely a direct result of the study protocol, and if the subject is in current, study approved treatment, for their eating disorder.

Participant safety will be managed in several ways. First, risk is managed through study eligibility criteria. Although we do not expect the hormone manipulation to elevate suicide risk based on previous studies,^{87, 88, 117, 118} as an added measure of safety, we exclude subjects who have a history of elevated suicide risk. Specifically, exclusionary criteria include a history of a suicide attempt. Second, risk is also managed by the truncated hormone regimen. The protocol has been shortened to only the amount of time necessary for each condition to elicit symptom change.

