Eligibility Screening: We will screen individuals remotely via Qualtrics and telephone as described in the original protocol. This includes screening individuals via phone or online Qualtrics screener. As previously approved, we were screening participants and adding them to a waitlist to be contacted once in-person visits resumed. Now that we are planning in-person visits, the individuals that were on the waitlist will be contacted to confirm study eligibility. A portion of the phone/clinic eligibility screener will be used to confirm eligibility. These participants will only be asked the menstrual cycle status and eating behaviors sections of the screener. In the event study activities need to be suspended again due to COVID19, we will resume use of the waitlist. This waitlist is a password-protected document that contains the potential subjects' name, temporary ID, and contact information.

Enrollment: If participants are deemed eligible based on their screening, we will follow-up with a remote Informed Consent (T0a) and a remote Clinical Health Screening and SCID Interview (T0b) visit. T0b will be scheduled after informed consent is obtained and the signed consent forms are received by study staff. No study procedures will be conducted until the signed consent forms are received by study staff. We also added 3 questions to the T0 questionnaires survey that assess the impacts of COVID-19 on eating behaviors.

Informed consent. The informed consent documents have been modified to reflect the changes to the study protocol outlined below. [name] or her trained study coordinator will obtain informed consent from those individuals who pass the initial screening and are interested in participating. Notably, the informed consent process during COVID (virtual/remote) will mirror the procedures for an in-person visit, the major difference being the visit will occur remotely via WebEx and the consent forms will be mailed, reviewed, signed, and mailed back. Participants will not review the consent documents on their own, but will be walked through the forms, verbatim, as would be completed during an in-person visit.

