Two copies of the consent forms will be mailed to the person in unmarked envelopes. For any participant that does not receive this most recent consent form, they will be given the COVID-19 Consent Addendum. This document includes text from the updated study consent form that discusses COVID-19 exposure risks and the measures that may be taken to prevent exposure.

Consent forms will be reviewed remotely during WebEx (or telephone if necessary) and will be returned to study staff signed in a pre-paid envelope. The participant will be given multiple opportunities to ask questions. Prior to signing the consent form, participants will be asked the consent quiz to ensure understanding of the consent form. We will obtain contact information and social security number verbally from the participant after the consent process. Contact information and social security number are only required if the participant consents to participate in the study. Future studies consent will also only be obtained verbally.

Regarding WedEx, it is HIPPA complaint, ISO/IEC 27001:2013 certified, and approved for the transmission of PHI. Visits will be password protected and only those with the password can enter the study visit. UNC SOM specifically recommends the use of WebEx for virtual research study visits.

Study Procedures and COVID19 Study Visit Modifications:

Screening Period Prior to Medication Administration. Prior to medication administration, participants complete a screening period which examines their eating disorder symptoms daily, during 1 menstrual cycle. No changes have been made to this aspect of the protocol as the original protocol included completing this screening virtually/remotely through daily Qualtrics surveys.

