Medication administration. Medication will be administered similar to our original protocol as in person contact is required (i.e., Lupron injection). However, for any study visits where giving the study participant their next set of oral medications is the *only in-person activity* needed, the study coordinator will pass off the pills directly to the participant during a drive by the participant's house. Alternatively, the participant can drive by the hospital and the research assistant will give them the pills when they pull up to the hospital. If the visit is already requiring in-person contact for another reason (i.e. Lupron injection or behavioral tasks), the personnel that is involved in the visit will give the participant the study pills.

Blood draws. Due to significant safety concerns regarding in-person contact and biological specimen processing and handling, all study blood draws will be removed from the protocol except those that are for labs in order to determine if participant is healthy and can participate in the study (T0). If the participant attends the research study gynecological exam (which must be conducted in person and cannot be modified), this will be collected during the exam. If they instead provide their own gynecological records, the blood draw for labs will be performed by the coordinator at the participant's home or at the hospital.

Saliva samples. Saliva samples will now be collected for E2 and P4 assay. This will be collected by the participant in their home. All saliva sample materials will be given to participants with instructions during the first in-person contact during (T1) to be completed remotely. We have created collection documents and a log for participants to complete in. At visit T4, all tubes will be collected from the participant and taken back to the UNC Core laboratory for storage. Consent forms have been modified to reflect this change.

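### The available text describes pregnancy testing only at screening, about one menstrual cycle before the first Lupron depot, with no repeat described at T1

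*Combined protocol and SAP*

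**What the plan says.** Pregnancy testing appears in two places, both as part of screening. Section 4.3 lists it among the eligibility steps and gives the reason: "No pregnant women will be entered into the study, because the study drugs (Lupron, estrogen, and progesterone) may be associated with birth defects". Section 6 (Screening) includes it in the T0 laboratory work: "This screening will include a laboratory panel (CMP, CBC, pregnancy test".

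The order of events after that is also stated. Section 6 (Screening) has enrolled women complete daily ratings for one natural cycle. Appendix B confirms that this comes before any drug: "Prior to medication administration, participants complete a screening period which examines their eating disorder symptoms daily, during 1 menstrual cycle". Section 6 (Medication Administration and Study Visits) then says "The first dose of Lupron will be given at T1 and monthly thereafter". Sections 5.2 and 6 place that injection at about day six of the cycle.

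The sampling provisions are these:

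- Table 4 marks venipuncture at T0 only and has no pregnancy-test row at any visit.
- Appendix B drops all study blood draws "except those that are for labs in order to determine if participant is healthy and can participate in the study (T0").
- Under Appendix B, screening includes "a remote Clinical Health Screening and SCID Interview (T0b) visit", so the blood is drawn separately: at the study gynecological exam, at home or at the hospital. No date or window is given.

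**The concern.** The protocol excludes pregnant women because the study drugs may harm a fetus. Exposure to those drugs begins at T1, not at T0. Between the described test and that first exposure lies a full ovulatory cycle, so a negative result at T0 does not directly establish status on the day of injection.

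Two features make T1 the natural checkpoint. First, the product is a depot: "Intramuscular injection of the depot formulation provides plasma concentrations of leuprolide over a period of one month". Once injected it cannot be withdrawn. Second, Lupron is given in order to stop the cycle (Section 1.1). After T1 a missed period is expected and no longer alerts anyone.

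What is at stake is participant safety. No estimate, test or power figure depends on it.

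**Working it through.** **1. Length of the gap.** The protocol does not state the T0 to T1 interval. It can be inferred from three inputs:

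- 17 weekly scores from T0 to T4 (Section 6, Daily Symptom Assessment).
- 91 days of daily surveys during the hormone challenge (Section 9.3).
- 4 weeks of Lupron alone, then 8 weeks of capsules (Section 5.2). Section 6 gives the same total: 6 weeks to T2, then 2 weeks of addback, 2 of washout and 2 of addback.

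Gap = (T0 to T4) − (T1 to T4).

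| Basis for T1 to T4 | Calculation | Gap |
|---|---|---|
| Paid survey days | 17 × 7 − 91 = 119 − 91 = 28 days | 4 weeks |
| Phase lengths | 17 − (4 + 8) = 17 − 12 | 5 weeks |

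As a consistency check, assume a natural cycle of 4 to 5 weeks. Adding a 12 to 13 week challenge gives 16 to 18 weeks, which brackets the stated 17.

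**2. Dependence on the sample date.** The 4 to 5 weeks assumes that the sample is taken at T0, as the order of the Screening paragraph implies. If it could be taken at any point from T0 to T1, the nominal range is 0 to 5 weeks. The available text sets no maximum interval between test and injection.

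**3. Search for a later test.**

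| Place | What it shows on pregnancy testing |
|---|---|
| Section 4.3 | Test at eligibility screening |
| Section 6, Screening | Test in the T0 panel |
| Section 6, Baseline (T1) | Questionnaires and tasks; no test |
| Section 6, Check-in Visits | Side effects and adherence; no test |
| Section 6, Medication Administration | Dosing schedule; no test |
| Table 4 | No pregnancy-test row; venipuncture at T0 only |
| Appendix B | Only T0 eligibility bloods retained |
| Section 4.4.1 | A clearance rule: "Participants with significant clinical/laboratory abnormalities will not be enrolled/discontinued from the study prior to GnRH agonist administration" |

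The Section 4.4.1 rule acts on laboratory results that exist. The only laboratory tests scheduled in the available text are at T0, so the rule does not itself create a retest.

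**4. Size of the change.** 15 participants × 1 test = 15 tests. The documents give no pregnancy rate, so no expected number of exposed pregnancies can be calculated.

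**The case against.** The strongest objection is that this is a claim of absence made on an incomplete text. Section 5.4, which sits inside the Study Drug chapter, is missing from the copy reviewed. So are the content of Figure 5 and the consent form. A pre-dose test may be stated in any of them. This stands. A reader might infer that the trial has no test at T1; the documents cannot show that.

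Table 4 is also weak evidence by itself. It has no row for the screening pregnancy test, which certainly takes place, nor for the Lupron injections or the Daily Rating Form. A missing row therefore does not prove a missing procedure. The venipuncture schedule says nothing about urine tests. This stands too, although Sections 3.1 and 6 direct the reader to Table 4 and Section 6 for the visit procedures, and neither describes a repeat.

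The plan already lowers the risk. Women must have regular cycles (Section 4.1). Those who are pregnant, planning pregnancy or unwilling to use barrier contraception are excluded (Section 4.2). Injection at about cycle day six follows a menses. These safeguards are real, and they make the residual risk low. But day six is written as a dosing-time rule and contraception as a willingness criterion. Neither is presented as confirmation of pregnancy status before the injection.

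A reader might also infer that women are dosed with no prior pregnancy test at all. That is wrong: the screening test in Section 6 precedes every dose. Nor should the single test simply be moved to T1. That would remove the entry check that Section 4.3 requires and let a pregnant woman complete about a month of study procedures before detection.

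**Conclusion.** The point holds within the available text. Pregnancy testing is described only at screening, one unsuppressed cycle follows, and no repeat is described before the first depot at T1. The interval is about 4 to 5 weeks if the sample is taken at T0, and nominally 0 to 5 weeks if its date is left open. Both figures are inferred.

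Residual risk is low, no number of pregnancies is claimed, and no analysis is affected. The conclusion is that a direct check at T1 is a worthwhile, inexpensive safety improvement that serves the protocol's own birth-defect rationale. Confidence is moderate, because Section 5.4 may already require the check.

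**What to change.** Keep the screening test. In addition, require a negative urine pregnancy test at T1 before the first Lupron injection, with one sentence in Section 6 and one row in Table 4 showing the test at T0 and T1. Repeats at later injections or before addback can be left to the investigator.

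The cost is 15 urine kits and a few minutes per participant. Appendix B already makes T1 an in-person visit, for the injection and the behavioral tasks. No blood draw is added, and blinding, sample size and analysis do not change. A kit that the participant runs and shows to staff would largely avoid Appendix B's concern about handling specimens.

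If Section 5.4 already requires a pre-dose test, conduct need not change and only the schedule should be updated to show it.
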